7.4.1 Blood sampling

Blood samples will be drawn at trough (before morning dose) at Week 2 (Visit 5), Week 4 (Visit 6) and Week 8 (Visit 7) [See Table 1]. Blood sampling will take approximately 1 minute. Procedures for sampling for PK and PD measurements are as follows: blood (4 mL for ACT-132577 measurements) will be collected by direct venipuncture or via an i.v. catheter placed in an antecubital vein in the arm in Vacutainer® or equivalent tubes containing K3-EDTA. Immediately following collection of the required blood volume, the Vacutainer® will be slowly tilted backwards and forwards (no shaking) to bring the anti-coagulant into solution, and immediately cooled in an ice water bath. Within 30 minutes of collection, the Vacutainer® will be centrifuged at approximately 1500 g for 10 minutes at 4 °C. The plasma for PK (approximately 1.5 mL) will be transferred into one labeled polypropylene tube to avoid carryover of erythrocytes. The PD plasma sample (about 500 μL) will be

^{*} If blood must be taken for hematology / clinical chemistry laboratory analysis, a serum pregnancy test must be performed.

Essential hypertension Protocol AC-080A201 Version 3 30 May 2016, page 64/112

Confidential

transferred into 1 labeled polypropylene tube. All samples will be stored in an upright position at -80 ± 20 °C. The date and exact actual clock time of collection of each blood sample will be entered in the eCRF as well as the exact dates and time of the drug administration prior and after blood draw.

7.4.2 Labeling and shipment

Details about the collection, sampling, storage, and shipment procedures can be found in the laboratory manual. Sites will receive required material from the central laboratory before the start of the study (e.g., tubes, labels, shipment materials). The site personnel will take care of the shipment of the plasma samples to central laboratory who will forward the PK samples to the bioanalytical laboratory at time intervals agreed with the sponsor.

7.4.3 Bioanalysis

ACT-132577 will be measured using liquid chromatography with tandem mass spectrometry by Actelion. The foreseen limit of quantification is 1 ng/mL.

Pharmacodynamic measurements of ET-1 will be measured in plasma by central laboratory after the study has clinically been completed.

8 SCHEDULE OF VISITS

Please refer to Table 1 for more details.

It is the responsibility of the investigator to obtain written informed consent(s) from each subject participating in this study after adequate explanation of the objective, methods, and potential hazards of the study [see Section 7.1].

Subjects without a confirmed diagnosis of mild-to-moderate hypertension are offered the possibility of having their BP measured (at trough if subjects are on anti-hypertensive treatment) with an automated office BP device (i.e., BpTRU) before entering the screening period.

In such cases, the specific written ICF ("Confirmation of mild-to-moderate hypertension by measuring blood pressure with an automated device") must be obtained before the BP measurement. If the subject has confirmed hypertension, he/she will be proposed to enter the study and a complete ICF provided.

The subject can only enter screening once the "study" ICF is signed.

It is permitted to re-screen subjects once, if the subject did not take any study medication and if the reason for non-eligibility was transient (e.g., abnormal laboratory test, insufficient wash-out period of a forbidden medication, etc.), provided that documented

Essential hypertension Protocol AC-080A201 Version 3 30 May 2016, page 65/112

Confidential

authorization has been received from Actelion. All screening assessments should then be repeated at the time of re-screening.

Unscheduled visits may be performed at any time during the study. Depending on the reason for the unscheduled visit (e.g., AE), appropriate assessments will be performed based on the judgment of the investigator and the results will be recorded in the eCRF. After an unscheduled visit, the regular scheduled study visits must continue according to the planned visit and assessment schedule.

To ensure compliance, at each visit the study personnel must remind women of childbearing potential to use the methods of contraception defined for this study. The reminders must be documented in the subject's chart.

8.1 Screening and run-in periods

Screening lasts up to 72 h, starting with the signature of the "study" ICF and lasting until the Visit 1 eligibility assessments (i.e., eligibility to enter the run-in period) are completed.

The run-in period takes place 4 to 6 weeks prior to Day 1 (Visit 4 / Randomization) and starts with the Screening visit (Visit 1) and ends with the Randomization visit. The run-in period is an SB placebo treatment period; the study staff must not inform the subjects about the treatment they are receiving during the run-in period.

The run-in period is 4 weeks for anti-hypertensive treatment naïve subjects at Screening (Visit 1). Visit 1 is combined with Visit 2.

The run-in period is 6 weeks for subjects on anti-hypertensive treatment at Screening (Visit 1), including a 2-week wash-out period for anti-hypertensive treatment. In such a case, anti-hypertensive treatment must be discontinued (according to label) at Visit 1 if there is no contra-indication to stop it.

8.1.1 Visit 1 / Week -6

Visit 1 starts with the subject signing the ICF and lasts up to 72 h, i.e., until eligibility assessments are completed.

The following assessments are to be performed at the Screening visit. It is recommended to perform the screening assessments in the following order; however the order can be adapted to site and subject convenience:

- Subject information and consent form.
- Access IRT to get a subject number. The subject number will identify the subject throughout the study. In case of re-screening [see Section 8.1], the subject number assigned during the first screening procedure will be retained.

Essential hypertension Protocol AC-080A201 Version 3 30 May 2016, page 66/112

Confidential

- Demographics: age, race/ethnicity, sex, and weight and height.
- Medical history and disease characteristics.
- Sitting BP and HR, and standing BP, measured by OBPM device.
 - Subjects on anti-hypertensive treatment(s) must have their BP measured at trough
 (i.e., before intake of anti-hypertensive treatment[s]). Therefore, the subject
 should be asked to withhold the anti-hypertensive treatment(s) dose(s) in the
 morning of BP measurement at site.
- Physical examination.
- 12-lead ECG: Historical ECG is acceptable if not older than 6 months. Otherwise, perform a 12-lead ECG.
- Assessment of childbearing potential and recording of contraception methods, if applicable.
- Laboratory tests: Historical blood laboratory analysis is accepted to check exclusion criterion 15, if not older than 3 months.
 - If historical laboratory data are available, perform a urine pregnancy test for women of child-bearing potential.
 - If historical laboratory data are not available, laboratory tests (i.e., hematology, blood chemistry) and **serum** pregnancy test (only for women of child bearing potential) must be performed.
- Recording of AEs and SAEs.
- Previous and concomitant medication.

The investigator must check inclusion/exclusion criteria and decide on the subject's eligibility for the study [see Sections 4.3 and 4.4, respectively].

If the subject is eligible:

- If the subject is treated with anti-hypertensive drugs and there is no contra-indication to stop these medications, stop all ongoing medications that can affect BP [see Section 5.2.4] according to their labels.
- Access IRT to get bottle numbers.
- Dispense the run-in period bottles. Instruct subject to take one capsule from each bottle irrespective of food intake every morning between 7:00 and 10.00 a.m.
- Study treatment intake at site.
- Remind the subject to bring back both bottles to the next visit and not take study treatment on the day of study visit prior to coming to the site.
- If judged necessary, provide a home BP device to the subject, instruct how to operate it, where to record the measured BP values, when to monitor BP and whom to contact [see Section 7.2.2], if necessary.

Essential hypertension Protocol AC-080A201 Version 3 30 May 2016, page 67/112

Confidential

• If subject was anti-hypertensive treatment-naïve, Visit 1 is combined with Visit 2 (i.e., Visit 2 does not take place), the next visit will be the Week –1 visit (Visit 3).

If the subject is not eligible:

- Date of eligibility assessment will be collected in the eCRF; additionally, the reasons for screening failure are documented in the eCRF (screening information is collected for all screen failure subjects).
- Subjects on anti-hypertensive treatment(s) who withhold the anti-hypertensive treatment(s) dose(s) for trough BP measurement should take the treatment at site.

8.1.2 Visit 2 / Week -4

This visit will be performed only for subjects who had anti-hypertensive drugs at Visit 1.

The visit will be performed at Day -28 ± 3 days.

The subject must not take study treatment at home on the morning of Visit 2.

Visit 2 includes:

- Sitting BP and HR, and standing BP, measured by OBPM device at trough.
- Physical examination and body weight.
- *Urine pregnancy test for women of childbearing potential.
- Reporting of AEs and SAEs.
- Recording of changes in concomitant medications.
- *Assessment of childbearing potential and recording of changes in contraception methods, if applicable.
- *Record the date and time of last study treatment intake before this visit.
- *Check compliance with study treatment.

The investigator checks the exclusion criteria and the following eligibility criterion and decides on the potential eligibility of the subject for the next visit (Visit 3):

- o mean SiDBP measured by OBPM device < 110 mmHg
- 1) If this criterion is not met, the subject must be discontinued from the study. In such case, tests highlighted by * are optional and performed as deemed necessary per medical practice. The investigator has to record the reason of the run-in failure in the eCRF. A follow-up telephone call must be performed in 2 weeks to check any potential AEs/SAEs.
- 2) If the criterion is met, study treatment must be taken at site (i.e., one capsule from each bottle) from the bottles dispensed at Visit 1. Record the study treatment intake date and time. Retrieve the 2 bottles.

Essential hypertension Protocol AC-080A201 Version 3 30 May 2016, page 68/112

Confidential

- Access IRT to get bottle numbers.
- Dispense 2 new bottles, and instruct subject to take one capsule from each bottle irrespective of food intake every morning between 7:00 and 10.00 a.m.
- Remind the subject to bring back both bottles to the next visit and not take study treatment on the day of study visit prior to coming to the site.

8.1.3 Visit 3 / Week -1

This visit will be performed at Day -7 ± 4 days.

The subject must not take study treatment at home on the morning of Visit 3.

Visit 3 includes:

- Sitting BP and HR, and standing BP, measured by OBPM device at trough.
- Physical examination and body weight.
- *Laboratory test (i.e., hematology, blood chemistry, and pregnancy test if applicable).
- Reporting of AEs and SAEs.
- Recording of changes in concomitant medications.
- *Assessment of childbearing potential and recording of changes in contraception methods, if applicable.
- *Record the date and time of last study treatment intake before this visit.
- *Check compliance with study treatment.

The investigator checks the exclusion criteria and the following eligibility criterion and decides on the potential eligibility of the subject for the next visit (Visit 4):

- o mean SiDBP measured by OBPM device < 110 mmHg
- 1) If this criterion is not met, the subject must be discontinued from the study. In such case, tests highlighted by * are optional and performed as deemed necessary per medical practice. The investigator has to record the reason of the run-in failure in the eCRF. A follow-up telephone call must be performed in 2 weeks to check any potential AEs/SAEs.
- 2) If the criterion is met, study treatment must be taken at site (i.e., one capsule from each bottle). Record the study treatment intake date and time and instruct subject to continue taking one capsule from each bottle irrespective of food intake every morning between 7:00 and 10.00 a.m. Remind the subject to bring back both bottles to the next visit and not take study treatment on the day of study visit prior to coming to the site.

Essential hypertension Protocol AC-080A201 Version 3 30 May 2016, page 69/112

Confidential

8.1.4 Visit 4 / Day -1 to Day 1

The assessments of this visit will be performed over 2 consecutive days.

Day -1: Visit 4 / Pre-randomization is the end of run-in period. At Day -1, eligibility criteria will be checked. Subjects who are eligible must perform the baseline 24-h ABPM under run-in period study treatment (placebo) before randomization on Day 1.

Day 1: Visit 4 / Randomization is the start of DB treatment period. The DB period consists of Visit 4 / Randomization to 7 / DB-EOT (i.e., Day 1, Week 2, Week 4, and Week 8 visits).

8.1.4.1 Day -1 (Visit 4 / Pre-randomization)

The Day -1 visit must be scheduled 7 days \pm 2 days after Visit 3.

Visit 4 / Pre-randomization includes:

- Sitting BP and HR, and standing BP, measured by OBPM device at trough.
- Physical examination and body weight.
- *12-lead ECG.
- *Laboratory tests (i.e., hematology, blood chemistry, and pregnancy test if applicable).
- *Urinalysis (dipstick by site / UACR by central laboratory).
- Reporting of AEs and SAEs.
- Recording of changes in concomitant medications.
- *Assessment of childbearing potential and recording of changes in contraception methods, if applicable.
- *Record the date and time of last study treatment intake before this visit
- Check compliance with study treatment.

The investigator checks the following eligibility criteria and decides on the eligibility of the subject for randomization:

- Mean SiDBP \geq 90 to < 110 mmHg measured by OBPM device.
- Treatment compliance ≥ 80% during run-in period.
- 1) If one of these criteria is not met, the subject must be discontinued from the study. In such case, tests highlighted by * are optional and performed as deemed necessary per medical practice. The investigator has to record the reason of the run-in failure in the eCRF. A follow-up telephone call must be performed in 2 weeks to check any potential AEs/SAEs.

Essential hypertension Protocol AC-080A201 Version 3 30 May 2016, page 70/112

Confidential

2) If all these criteria are met, perform the following:

- Apply the ABPM device according to the BP manual for 24 h recording and review the subject's instruction handout with the study participant.
- Administer the last doses of the run-in period study treatment. Record the study treatment intake date and time and retrieval of study treatment bottles.
- Instruct subject to return to the site the next morning.

8.2 Double-blind period

8.2.1 Day 1 (Visit 4 / Randomization)

Day 1 is the start of DB treatment period for subjects eligible after Day -1 assessments (Visit 4 / Pre-randomization).

Day 1 includes:

- Remove the 24-h ABPM device.
- Reporting of AEs and SAEs.
- Recording of changes in concomitant medications.
- Access IRT and obtain randomization and bottle numbers. Dispense the DB period study treatment.
- Instruct subject to take one capsule from each bottle irrespective of food intake every morning between 7:00 and 10:00 a.m.
- Study treatment intake at site.
- Remind the subject to bring back both bottles to the next visit and not take study treatment on the day of study visit prior to coming to the site.

8.2.2 Visit 5 / Week 2

This visit will be performed at Day 14 ± 3 days. The subject must not take study treatment at home on the morning of Visit 5.

Visit 5 includes:

- Sitting BP and HR, and standing BP, measured by OBPM device at trough.
- Physical examination and body weight.
- Laboratory test (i.e., hematology, blood chemistry, and pregnancy test if applicable).
- •
- Urinalysis (dipstick by site / UACR by central laboratory).
- Reporting of AEs and SAEs.
- Recording of changes in concomitant medications.

Essential hypertension Protocol AC-080A201 Version 3 30 May 2016, page 71/112

Confidential

- Assessment of childbearing potential and recording of changes in contraception methods, if applicable.
- Record the date and time of last study treatment intake before this visit.
- Check compliance with study treatment.
- Study treatment intake at site. Record the study treatment intake date and time.
- Instruct subject to continue taking one capsule from each bottle irrespective of food intake every morning between 7:00 and 10:00 a.m.
- Remind the subject to bring back both bottles to the next visit and not take study treatment on the day of study visit prior to coming to the site.

8.2.3 Visit 6 / Week 4

This visit will be performed at Day 28 ± 3 days. The subject must not take study treatment at home on the morning of Visit 6.

Visit 6 includes:

- Sitting BP and HR, and standing BP, measured by OBPM device at trough.
- Physical examination and body weight.
- 12-lead ECG.
- Laboratory test (i.e., hematology, blood chemistry, and pregnancy test if applicable).
- Urinalysis (dipstick by site / UACR by central laboratory).
- Reporting of AEs and SAEs.
- Recording of changes in concomitant medications.
- Assessment of childbearing potential and recording of changes in contraception methods, if applicable.
- Record the date and time of last study treatment intake before this visit.
- Check compliance with study treatment and retrieve study treatment bottles.
- Access IRT to obtain new bottle numbers and dispense 2 new study bottles.
- Study treatment intake at site. Record the study treatment intake date and time.
- Instruct subject to take one capsule from each bottle irrespective of food intake every morning between 7:00 and 10:00 a.m.
- Remind the subject to bring back both bottles to the next visit and not take study treatment on the day of study visit prior to coming to the site.

Essential hypertension Protocol AC-080A201 Version 3 30 May 2016, page 72/112

Confidential

8.2.4 Visit 7 / Week 8 DB-EOT

The assessments of this visit will be performed over 2 consecutive days.

Visit 7 / Part 1 is the end of DB treatment period. On this day, the EOT 24-h ABPM under DB study treatment will be performed.

Visit 7 / Part 2 is the start of the SB placebo withdrawal period.

8.2.4.1 Visit 7 / Part 1

Visit 7 / Part 1 must be scheduled at Day 55 ± 5 days.

Part 1 includes:

- Sitting BP and HR, and standing BP, measured by OBPM device at trough.
- Physical examination and body weight.
- 12-lead ECG.
- Laboratory test (i.e., hematology, blood chemistry, and pregnancy test if applicable).
- |
- Urinalysis (dipstick by site / UACR by central laboratory).
- Reporting of AEs and SAEs.
- Recording of changes in concomitant medications.
- Assessment of childbearing potential and recording of changes in contraception methods, if applicable.
- Record the date and time of last study treatment intake before this visit.
- Check compliance with study treatment.
- Apply the ABPM device according to the BP manual for 24-h recording and review the subject's instruction handout with the study participant.
- Intake of the last doses of the DB period study treatment and retrieve study treatment bottles. Record the study treatment intake date and time.
- Instruct subject to return to the site in the next morning.

8.3 Withdrawal period

8.3.1 Visit 7 / Part 2

Visit 7 / Part 2 is the start of SB placebo withdrawal period.

This period is a SB treatment period, the study staff must not inform the subjects about the treatment they are receiving during this period.

Part 2 includes:

Remove the 24-h ABPM device.

Essential hypertension Protocol AC-080A201 Version 3 30 May 2016, page 73/112

Confidential

- Reporting of AEs and SAEs.
- Recording of changes in concomitant medications.
- Access IRT and obtain bottle numbers. Dispense the withdrawal period study treatment (placebo).
- Study treatment intake. Record the study treatment intake date and time.
- Instruct subject to take one capsule from each bottle irrespective of food intake every morning between 7:00 and 10:00 a.m.
- Remind the subject to bring back both bottles to the next visit and not take study treatment on the day of study visit prior to coming to the site.

8.3.2 Visit 8 / Week 10 withdrawal EOT

The visit will be performed at Day 70 ± 3 days. The subject must not take study treatment at home on the morning of Visit 8.

Visit 8 includes:

- Sitting BP and HR, and standing BP, measured by OBPM device at trough.
- · Physical examination and body weight.
- 12-lead ECG.
- Laboratory test (i.e., hematology, blood chemistry, and pregnancy test if applicable).
- Urinalysis (dipstick by site / UACR by central laboratory).
- Reporting of AEs and SAEs.
- Recording of changes in concomitant medications.
- Assessment of childbearing potential and recording of changes in contraception methods, if applicable.
- Record the date and time of last study treatment intake before this visit.
- Retrieve study treatment bottles.
- Check compliance with study treatment.
- If home BP device provided to the subject, retrieve the device.
- Make an appointment for the follow-up telephone call, or, for women of childbearing potential, an appointment for the follow-up visit.

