A blinded sample size re-estimation will be performed by the sponsor after 100 subjects have been randomized and their Week 8 BP data are available for analysis. The sample size will be recalculated considering the overall SD of the primary endpoint (change from baseline to Week 8 in mean trough SiDBP, measured by OBPM) in the PPS. The recalculated size of the PPS is expected to be between 280 subjects and the originally foreseen 420 subjects. The associated number of subjects to be randomized will also be re-estimated and is expected to be between 300 subjects and the originally planned 540 subjects. See Section 11.5.3 for more details.

STUDY COMMITTEES

An Independent Liver Safety Data Review Board (an external expert committee of hepatologists) provides ongoing assessment and advice regarding any hepatic events that may require further evaluation during the study.

ACT-132577 Essential hypertension Protocol AC-080A201 Version 3 30 May 2016, page 29/112

Table 1 Visit and assessment schedule

PERIODS	Name / duration	Period I: Run-in / 4–6 weeks ⁶				Period II: Double-blind / 8 weeks				Period III: withdrawal / 2 weeks		Premature EOT		Follow-up
VISITS	Number Name	1 ⁶ Week –6	2 ⁶ Week –4	3 Week -1	4		5 Week 2	6 Week 4		7 ek 8	8 Week 10	9	U1, 2, 3, etc. ¹⁰	Telephone call ⁹ or visit ¹¹
	Name	Screening**			Randomization				DB-	-EOT	WD-EOT	Within 7 days	Unscheduled	EOS
	TIME / Week	Day -42	Day -28 (± 3 d)	Day -7 (± 4 d)	Pre- Day-1	Day 1	2 Day 14 (± 3 d)	4 Day 28 (± 3 d)	Part 1 Day 55 (± 5 d)	Part 2 Day 56	10 Day 70 (± 3 d)	after last study treatment intake	Any time	30–33 d after last dose of DB treatment
Infor	Informed consent													
Eligibility		X	X	X	X									
Med	Medical history													
Physica	Physical examination		X	X	X		X	X	X		X	X	X	
Concomi	Concomitant medications		X	X	X	X	X	X	X	X	X	X	X	X
HR*, bod	HR*, body weight, height1		X	х	X		X	X	X		X	X	X	
12-lead ECG	12-lead ECG*				X ⁹			X	X		X	X ⁹	X	
Laboratory in	Laboratory incl. pregnancy tests*2			X ⁹	X ⁹		X	X	X		X	X ⁹	X	X 2
U	Urinalysis		X ^{7, 9}		X ⁹		X	X	X		X	X ⁹	X	
Office BP measurement*		X	X	X	X		X	X	X		X	X	X	
Home	e BP device ¹²	X											>	
Ambulatory BP measurement*					X				X					
PK and PD sampling ¹³							X	X	X					
Compliance	Compliance with study treatment		X ⁹	X9	X		X	X	X		X	X	X	
Study treatment dispensing/return		X	X ⁸		X	X		X	X	X	X	X	X	
Adverse events ³		X	X	X	X	X	X	X	X	X	X	X	X	X
Serious adverse events ³		X	X	X	X	X	X	X	X	X	X	X	X	X

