Period III is a SB placebo period of 2 weeks which starts at Visit 7 / Part 2 with the first dose of withdrawal (WD) study treatment (placebo), and ends at Visit 8 (WD-EOT).

Follow-up period

The follow-up period starts after the last dose of SB withdrawal study treatment (placebo) and ends at least 2 weeks (i.e., 30 days after the last dose of the DB treatment) thereafter, by the follow-up telephone call, or follow-up visit only for women of childbearing potential to perform the pregnancy test at the site.

End-of-Study

End-of-Study (EOS) for a single subject is defined as the date of the follow-up telephone call or follow-up visit.

If a subject withdraws consent and does not wish to participate in the study visits, the date of consent withdrawal is EOS for this subject. If a subject is declared lost to follow-up [see also Section 9.2], date of last contact is EOS for this subject.

In addition, unscheduled visits may take place at any time during the study, in which case appropriate assessments [as specified in Table 1] may be performed at the discretion of the investigator and must be recorded in the electronic Case Report Form (eCRF).

At the end of the study, the investigator/delegate will explain to the subject what treatment(s)/medical care is necessary and available according to local regulations.

Study duration

[figure not shown]
Subject participation in the study will be up to 16–18 weeks.

The overall study design is depicted in Figure 1.

Essential hypertension Protocol AC-080A201 Version 3 30 May 2016, page 37/112

Confidential

Figure 1 Study design

^{*}SB placebo run-in period is 4 weeks for anti-hypertensive treatment naïve subjects; Visit 1 is combined with Visit 2.

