5.1.4.3 Withdrawal period (single-blind placebo)

All subjects will receive 2 bottles; one bottle contains placebo capsules matching ACT-132577 and the other bottle contains placebo capsules matching lisinopril. The subjects must be instructed to take one capsule from each bottle (i.e., total of 2 capsules) o.d. every morning from the morning of Visit 7 / Part 2 (i.e., after completion of the DB-EOT 24-h ABPM recording) to the morning of the day before Visit 8 (i.e., the WD-EOT visit). The WD period is an SB period (subject-blinded). Accordingly, site staff must not inform the subject of the treatment received during this period.

Essential hypertension Protocol AC-080A201 Version 3 30 May 2016, page 45/112

Confidential

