8.5 Follow-up period

A follow-up telephone call must be performed 30 days after the last dose of the DB treatment and the following must be checked with the subject:

- Any changes in concomitant medication.
- Any AEs and SAEs.

For women of childbearing potential:

A visit must be scheduled 30 days after the last dose of the DB treatment instead of telephone call to perform a serum pregnancy test, in addition to the above mentioned assessments.

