2 STUDY DESIGN AND FLOW

2.1 Study design

Study AC-080A201 is a prospective, multi-center, double-blind, double-dummy, randomized, placebo- and active-reference, parallel group, Phase 2 dose-finding study with ACT-132577 in subjects with essential hypertension (grade 1 and 2).

Approximately 1000 subjects are enrolled into the study, in order to have at least 540 subjects randomized in the 6 following groups using a 1:1:1:1:1:1 ratio: placebo, 5 mg ACT-132577, 10 mg ACT-132577, 25 mg ACT-132577, 50 mg ACT-132577 and lisinopril 20 mg. At least 420 subjects are expected to complete the trial. There are no stratification factors.

The study consists of the following study periods:

Screening

The screening period starts with the signature of the “study” informed consent form and lasts until Visit 1. During this period study assessments (e.g., laboratory test) are performed to determine whether the subject is eligible for the study.

Run-in period (Period I)

Period I is a single-blind (SB) placebo period of 4 to 6 weeks starting at Visit 1 and ends at Visit 4 / Randomization (after completion of the baseline 24-hour ambulatory blood pressure monitoring [ABPM] recording on the last dose of SB study treatment [placebo]).

The run-in period lasts 4 weeks for anti-hypertensive treatment naïve subjects.

The run-in period lasts 6 weeks for subjects on anti-hypertensive treatment including a 2-week wash-out period for anti-hypertensive treatment. The anti-hypertensive treatment must be discontinued (according to its label) at Visit 1, if there is no contraindication to stop it.

Treatment period (Period II)

Period II is a double-blind (DB) treatment period of 8 weeks which starts at Visit 4 with the first dose of DB study treatment and ends at Visit 7 at the first dose of SB withdrawal treatment.

Withdrawal period (Period III)

Period III is a SB placebo period of 2 weeks, which starts at Visit 7 with the first administration of first placebo dose (withdrawal [WD] study treatment) and ends at Visit 8 (WD-End-of-Treatment [EOT]).

Follow-up period

The follow-up period, including follow-up telephone call, or follow-up visit only for women of childbearing potential to perform the pregnancy test at the site, starts after the last dose of SB WD study treatment (placebo) and ends at 30–33 days after the last dose of the DB treatment.

End-of-Study (EOS)

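### Visit 8 is timed from double-blind start rather than from Visit 7, so the visit windows permit a stated 2-week withdrawal period to run from 6 to 22 days; a minor point with a nearly free fix

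*Protocol*

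**What the plan says.** Protocol 3.1 states: "Period III is a SB placebo period of 2 weeks which starts at Visit 7 / Part 2". The period ends at Visit 8, and Protocol 3.2 gives its purpose as looking for rebound in blood pressure after withdrawal.

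The visits are scheduled separately:

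- Protocol 8.2.4.1: "Visit 7 / Part 1 must be scheduled at Day 55 ± 5 days". The last double-blind dose is taken at Part 1, and Part 2 is the next day.
- Protocol 8.3.2: "The visit will be performed at Day 70 ± 3 days".
- Protocol 5.1.4.3: withdrawal placebo runs "to the morning of the day before Visit 8 (i.e., the WD-EOT visit").

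SAP Table 5 counts days from the start of double-blind treatment. Its Visit 8 analysis window opens 25 hours and 1 minute after end of treatment and has no upper limit.

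Follow-up brings in a second constraint. Under Protocol 3.1 it starts after the last placebo dose and "ends at least 2 weeks (i.e., 30 days after the last dose of the DB treatment) thereafter". Table 1 of the protocol gives "30–33 d after last dose of DB treatment", and SAP 2.1 likewise says it "ends at 30–33 days after the last dose of the DB treatment". Protocol 8.5 names a single day: "A follow-up telephone call must be performed 30 days after the last dose of the DB treatment".

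**The concern.** Nothing in 8.3.2 ties Visit 8 to the date on which Visit 7 actually took place. A site can keep both visit windows and still give a withdrawal period well short of, or well beyond, two weeks. The SAP windows do not correct this: whatever falls after end of treatment is analysed as Week 10, that is, Week 2 of withdrawal.

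The rebound endpoints (change from baseline, and from Week 8, to Visit 8 in sitting diastolic and systolic pressure) rest on this single visit. If time off drug varies widely, they mix subjects at different stages of washout. Visit-based withdrawal data (laboratory tests, ECG, weight, blood pressure) have the same problem. Some permitted combinations also leave too little time for the two-week gap before follow-up.

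**Working it through.** **Inputs.** Part 1 day P = 50 to 60 (11 days; Protocol 8.2.4.1). Part 2 = P + 1. Visit 8 day V = 67 to 73 (7 days; Protocol 8.3.2). Half-life about 44 h in healthy subjects (Protocol 1.2.1). Let w = V − P − 1, the days from Part 2, and d = V − P = w + 1, the days since the last double-blind dose.

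**The plan's own figure.** Nominally 70 − 56 = 14 days, so the stated two weeks reproduces. Nominal follow-up also fits: last placebo dose on Day 69, follow-up on Day 55 + 30 = 85, a gap of 16 days.

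**Range from the visit windows alone.** Shortest: 67 − 61 = 6 days from Part 2 (d = 7). Longest: 73 − 51 = 22 days (d = 23). There are 11 × 7 = 77 day pairs.

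**Effect of the follow-up rule.** The last placebo dose falls d − 1 days after the last double-blind dose. Follow-up on day F must satisfy F − (d − 1) ≥ 14, so d ≤ F − 13.

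- F = 33: d ≤ 20, so at most 19 days from Part 2. Pairs with d = 21, 22, 23 number 3 + 2 + 1 = 6 of 77.
- F = 30: d ≤ 17, so at most 16 days from Part 2. Pairs with d = 18 to 23 number 6 + 5 + 4 + 3 + 2 + 1 = 21 of 77.

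**What a site aiming for 14 days gets.** Exactly 14 days needs V = P + 15, which lies in Day 67–73 for P = 52 to 58. For the other four dates the nearest permitted day gives:

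| Part 1 day | Nearest Visit 8 | Days from Part 2 |
|---|---|---|
| 50 | 67 | 16 |
| 51 | 67 | 15 |
| 59 | 73 | 13 |
| 60 | 73 | 12 |

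Every Visit 7 date therefore allows 12 to 16 days (d = 13 to 17), which also meets the two-week rule with follow-up at exactly 30 days.

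**If Visit 8 were booked independently of Visit 7.** The documents do not give the actual visit spread, so these are assumed scenarios.

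- Uniform use of both windows: 77 − 6 = 71 pairs remain with d ≤ 20, and 77 − 21 = 56 with d ≤ 17. Pairs with d < 13 number 1 + 2 + 3 + 4 + 5 + 6 = 21; pairs with d = 18 to 20 number 6 + 5 + 4 = 15. The share outside d = 13–17 is 36/71 = 51% or 21/56 = 38%. The share outside d = 12–18 is 24/71 = 34% or 15/56 = 27%.
- Triangular use (weights 1..6..1 and 1..4..1): the share outside d = 12–18 is 22% (d ≤ 20) or 15% (d ≤ 17).
- Nominal days kept, or the nearest permitted day chosen: 0% outside either range.
- The SD of days off drug is 2.2 to 3.3 across the independent scenarios. With d uniform on 13–17 it is √2 = 1.4.

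**Residual drug.** The fraction of steady-state trough remaining is 0.5^((d − 1) × 24/44).

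- d = 7: 0.1035, about 5.2 mg-equivalent in the 50 mg arm.
- d = 15 (nominal): 0.0050, or 0.25 mg.
- Mean in the 50 mg arm under independent booking: 0.46–0.54 mg (triangular) or 0.67–0.83 mg (uniform).
- d uniform on 13–17: mean of 0.0107, 0.0073, 0.0050, 0.0034 and 0.0024 = 0.0058, or 0.29 mg.

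Only 0.2% to 1.8% of subjects would be at d = 7 in the independent scenarios.

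**The case against.** The strongest reply is that the protocol does state the duration. Two weeks appears in 3.1, in 3.2 and in the heading of the withdrawal column in Table 1. A site that honours it within Day 67–73 misses 14 days by at most two. A reader might infer from the 4 of 11 Visit 7 days on which exactly 14 cannot fit that the period fails for a third of subjects. The documents do not support that: the miss is 1 or 2 days. Nor do they show that Visit 8 was booked independently of Visit 7, which every non-zero percentage above assumes.

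A reader might also infer that early visits hide rebound. That is not demonstrated. Mean residue is under 1 mg-equivalent in the highest-dose arm. Even the 7-day extreme leaves about 5 mg-equivalent, and Protocol 5.1.1 reports that at 5 mg ET-1 did not differ from placebo (ET-1 is only a marker). The windows are the same in every arm.

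This reply disposes of any claim of serious harm. What stands is narrower: 8.3.2 gives sites no instruction to use the actual Visit 7 date, the short end has no explicit limit other than the stated duration, and some pairs inside both visit windows cannot meet the follow-up rule.

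**Conclusion.** The point holds as a minor, cheap improvement. The 6-to-22-day range, the caps of 19 and 16 days, and the 6 and 21 of 77 pairs are exact consequences of the written windows. How often the extremes occur is unknown: under the assumed scenarios the share outside 12–18 days since the last dose runs from 0% to 34%. The residue figures also assume that the healthy-subject half-life applies to these subjects.

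The effect is added heterogeneity in the Week 10 contrasts, which are listed among the other efficacy endpoints and are exploratory under SAP 10.1, and in measures taken at the withdrawal visit. Adverse-event collection runs to 30 days after double-blind discontinuation whatever the Visit 8 date. The primary endpoint, alpha and power are untouched.

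**What to change.** In Protocol 8.3.2 and Table 1, schedule Visit 8 at Visit 7 / Part 2 + 14 ± 2 days, which is 13 to 17 days since the last double-blind dose. The last placebo dose is then at most 16 days after the last double-blind dose, and 16 + 14 = 30, so the two-week rule is met even with follow-up at exactly 30 days. A ± 3 window would not do: at + 17 days the earliest compliant follow-up is day 17 + 14 = 31. Protocol 8.1.4.1 already times the Day −1 visit from Visit 3, so the approach is not new to sites.

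The cost is a wording change with no extra visit, a window one day narrower on each side, and a Visit 8 that may fall anywhere from Day 51 + 12 = 63 to Day 61 + 16 = 77 counted from double-blind start.

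SAP 4.2 shows that the SAP text post-dates database lock, so for data already collected the visit rule cannot change. There, tabulate days since the last double-blind dose at Visit 8 by arm, from dates the SAP already derives (11.6 to 11.8). Then repeat the Week 8 to Week 10 contrasts in subjects close to 14 days off drug, for example 13 to 17 days since the last dose. Under the assumed scenarios that subset loses between 0% and 51% of subjects; a 12-to-18-day subset loses at most 34%.
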